- 4) UA dipsticks will be used in office to evaluate for pH and specific gravity dipsticks are within 0.5 pH effective accurate compared to pH meters.^[21] Dipstick analysis should be done as soon as possible after the urine is collected as pH changes the longer it is left out as a result of the natural breakdown of urea.^[12] It will be analyzed by study coordinators. Samples will also be sent to lab for evaluation of chemical composition of creatinine, citrate, and calcium. Electrolytes will be indexed against creatinine to evaluate their concentrations without having a 24-hour void volume amount.^[5, 9] A pH-meter will also be used to correlate the accuracy of pH values reported by the dipsticks.
- 5) All urines will be frozen immediately upon acquisition until batch sent to Litholink for electrolyte and pH analysis. [10, 17] All samples will only be identifiable by the study identification number. The lab will be instructed to discard all samples after the necessary tests are conducted.
- 6) A sample of citrate-Poland Spring will be sent to Litholink for analysis of Calcium and Citrate for reference.

C. SUBJECT POPULATION

- Healthy adult subjects will be accrued from outpatient urology office employees, residents, medical students, and faculty members who volunteer to participate in the study. A recruitment flyer will be posted in the outpatient Urology office and given to interested persons. A recruitment email will also be sent to office personnel, residents, medical students and faculty.

- The study will recruit 20-30 subjects.

D. DATA ANALYSIS

- Data collected with respect to subject demographics will include that from the questionnaire, including use of medications that affect kidney excretion, body weight and height, age, history of kidney disease or stones, types of diet, and supplements use. These points will be linked with the subject's urinalysis and urine chemistry results, however the subject's name will be removed during the statistical analysis. Data will be stratified by these demographics to identify any patterns that could potentially be studied by future studies.
- Those subjects who identify as having renal disease/history of nephrolithiasis, or who take diuretics will be excluded from the study. Those who are required to be on a fluid restriction for their health will not be allowed to participate in the study for safety reasons. Those that do not have voids at the appropriate time intervals will also be excluded.

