- Data analysis will be conducted by [name] and [name] at Albany Medical Center.
- All questionnaires and diaries will be kept in research office, input into password-protected software, and analyzed at Albany Medical Center.
- Data Points: After discussing data points with [name] the study will aim to recruit at least twenty subjects, which will give 87% power to detect a difference in any urine variable that is at least as large as one standard deviation of that variable in the normal fluid intake session (two tailed alpha of 0.05). Since, assuming a normal distribution, one standard will encompass 68% of patients, we consider a one standard deviation difference to be the minimally important clinically significant difference in these measures. Data points will be statistically analyzed by a repeated measures ANOVA test. Further, changes in the below variables after doubling fluid intake will be calculated for statistically significant changes compared to normal fluid intake.
 - o pH
 - o Specific gravity,
 - o Calcium
 - o Creatinine
 - Citrate
 - o Changes in the above after doubling fluid intake

E. RISKS

- There are minimal risks to this study.
- If subjects are on a fluid restricted diet, the second component of the study could potentially be harmful to their health. For this reason, these subjects will be excluded from the study
- There is a risk that there is a violation of privacy due to a breach in study data. However, the data will not be able to be linked to a specific individual.
- There is a risk of exposing underlying illness while evaluating urines of otherwise healthy subjects.

F. BENEFITS

- The main benefits of this study are to improve the quality of care provided to stone-forming patients in the urologic clinical setting.

- Add to the general medical knowledge about urine composition and its variation.

G. CONFIDENTIALITY

- After consent is collected, all subjects will receive and be referred to by a study number ie. 1, 2, etc., which all collected specimens and documentations will utilize. The master key containing the names and corresponding study numbers will be securely stored on an AMC network drive to which only the research staff have access. The master key will be destroyed after all data collection and analysis.
- A portion of the subjects' past medical history and current medication regimens will be collected, but their name will be replaced by a study ID# to de-identify the data please see questionnaire.

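### Section D makes one SD the smallest clinically important difference for every urine variable because one SD covers 68% of people; that does not follow, and no variable has a clinical anchor

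*Combined protocol and SAP*

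**What the plan says.** Section D, Data Points, gives the sample-size argument. The plan states that "the study will aim to recruit at least twenty subjects". For this number it claims a power figure, "which will give 87% power to detect a difference in any urine variable", and it defines the size of the difference to be detected as "at least as large as one standard deviation of that variable in the normal fluid intake session". The test level is a "two tailed alpha of 0.05". Section C gives the recruitment range: "The study will recruit 20-30 subjects".

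Section D then justifies the target: "Since, assuming a normal distribution, one standard will encompass 68% of patients", and from this it concludes that "we consider a one standard deviation difference to be the minimally important clinically significant difference in these measures". The same bar applies to pH, specific gravity, calcium, creatinine and citrate.

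The planned analysis is a repeated measures ANOVA, plus a test of the changes from normal to doubled intake in the same subjects. Hypothesis 2 (end of Section A) has two halves: more fluid lowers urinary concentration, and calcium excretion stays the same. The documents give no SD in natural units, no within-person correlation or SD of change, no clinical threshold for any variable, and no equivalence margin for calcium.

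**The concern.** The premise concerns spread between people. The conclusion concerns how small a change within a person is worth noticing. The first does not imply the second: that about two thirds of volunteers lie within one SD of the mean does not show that a shift of less than one SD is harmless or uninteresting. Nor is one SD small. Under the same normality assumption it moves the median subject to the 84th percentile of the normal-intake distribution.

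This matters because it is the only importance threshold in the plan and also the justification for the sample size. A reader of the results could take a clear, statistically significant shift of less than one SD as falling short of clinical importance. The calcium half of Hypothesis 2 is the most exposed. A claim of no change depends on what size of change has been ruled out, and the plan supplies only a significance test and the one-SD bar.

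**Working it through.** **Inputs.** From Section D: n = 20, difference = 1 SD of the normal-intake distribution, two-sided alpha 0.05, stated power 87%. From Section C: up to 30 subjects. Assumed, because the documents do not give them: equal SD under both intakes, and within-person correlation rho from 0 to 0.7.

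**1. Reproduce the 87%.** Unpaired t-test, 20 v 20, 38 df: noncentrality = 1/sqrt(2/20) = 3.16, giving power of 86.9%. This matches. A paired t-test with n = 20 uses SD of differences = SD × sqrt(2(1 − rho)). It gives 85.1% at rho = 0, 94.8% at 0.3 and 98.9% at 0.5, and it gives 87% only near rho = 0.06. The stated figure therefore behaves like an unpaired calculation.

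**2. Smallest observed difference reaching p<0.05** (critical t × standard error).
- Unpaired, 20 v 20: 2.024 × sqrt(2/20) = 0.64 SD.
- Paired, n = 20: 2.093 × sqrt(2(1 − rho)/20).

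| rho (assumed) | Smallest significant difference |
|---|---|
| 0 | 0.66 SD |
| 0.3 | 0.55 SD |
| 0.5 | 0.47 SD |
| 0.7 | 0.36 SD |

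With 30 subjects, the paired figures run from 0.53 SD (rho = 0) to 0.29 SD (rho = 0.7). In each case there is a band of significant results below the plan's minimum.

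**3. What this means for calcium.** The 95% CI half-width equals the figure in step 2.
- Observed shift of 0.9 SD: the CI is 0.9 ± 0.64 = 0.26 to 1.54 SD on the plan's basis, and 0.9 ± 0.36 = 0.54 to 1.26 SD if paired with rho = 0.7. Zero is excluded, yet the shift is below the bar.
- Observed shift of 0.3 SD: the CI is 0.3 ± 0.64 = −0.34 to 0.94 SD, or 0.3 ± 0.36 = −0.06 to 0.66 SD. This is not significant, yet shifts well above 0.5 SD are not ruled out.

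Neither the one-SD bar nor non-significance alone supports a claim of no change. The CI shows what has been excluded.

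**The case against.** The strongest reply is that the sentence serves only to justify the sample size. The analysis that follows is by significance testing, and nowhere does the plan say that results below one SD will be called unimportant, or that calcium will be declared unchanged if it moves by less than one SD. A reader might infer such a rule from the wording, but it is not there. That stands, so the consequence is a risk of misreading and not a planned misclassification.

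A second reply is that comparing a time-of-day shift with the spread between people has some meaning where the aim is to validate clinic spot urines. That is fair as a reason to show results in SD units as well. It does not make one SD a clinical minimum, and it is not the reason the plan gives.

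A reader might also infer three stronger points that the documents do not support:
- *That the bar is about twice the smallest significant change.* On the plan's own figures the ratio is 1/0.64, about 1.6. A ratio of 2 at n = 20 needs a within-person correlation near 0.43, which is not stated. A ratio above 1 is no defect in any case: every design with more than 50% power has one.
- *That the SD is inflated by pooling the four daily collections.* Section D does not say that it is pooled.
- *That dipstick imprecision sets the pH bar.* Section B also provides a pH meter (item 4) and laboratory pH (item 5).

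**Conclusion.** The point holds as one of justification and wording. The 68% figure cannot establish a smallest important within-person change, and nothing else in the plan anchors one for any of the five variables. Differences from about 0.64 SD (the basis that reproduces 87%), or from 0.66 down to 0.36 SD (paired, n = 20, assumed correlations 0 to 0.7), would be statistically significant while lying below the plan's stated minimum, and could be read as unimportant. Hypothesis 2's calcium claim is left without a sound basis for concluding no change.

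The non sequitur depends on no assumption. The width of the band depends on equal SDs and on a correlation that the documents do not give. No planned test is invalid on this ground, and no revised sample size can be computed without a replacement difference and an SD of within-person change.

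**What to change.** In Section D:
- Delete the inference from 68%, and describe one SD only as the effect size used for planning.
- Report, for each variable, the mean within-person change with its 95% CI in natural units: pH units, specific gravity units, calcium and citrate per creatinine, and creatinine itself in concentration units.
- State that the calcium half of Hypothesis 2 will be judged from that CI, and not from non-significance or the one-SD bar.
- State that a difference below one SD will not be called unimportant on that ground alone.

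The change needs no extra subjects, samples or tests. Its cost is that the sample-size statement becomes less favourable, because 87% power then applies to a fairly large planning effect and no longer to the smallest change of interest. As an illustration only, power for 0.5 SD with 20 subjects is 34% on the unpaired basis, and 32%, 43%, 56% and 78% for a paired test at assumed correlations of 0, 0.3, 0.5 and 0.7.
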